Visit 2: Medication Start Visit: Qualifying subjects will return for a medication start visit and DEXA scan for body composition and estimation of daily caloric needs. Subjects will be trained in the use of a CGM system (Dexcom G4 Platinum). The monitor will be in real time unblinded mode throughout the uptitration portion of each study phase for safety purposes by guarding against hypoglycemia due to insulin sensitization and allowing informed insulin dose adjustment with assistance from study personnel if needed. Baseline insulin dosing totals and average blood glucose will be recorded by subjects 3 days prior to starting the study medication. Subjects will also complete hypoglycemia and sleep questionnaires to assess frequency and awareness of lows, sleep patterns and sleep adequacy. Medication will be dispensed by the UCH or CHCO pharmacy to blind subjects and study personnel. Subjects will uptitrate study medication as follows: BCQR (0.8 mg) or placebo- 1 pill QAM for one week, then 2 pills QAM for one week, then 4 pills QAM for the remainder of the 4 weeks. If an uptitration step is not tolerated, subjects will be returned to the last tolerated dose for a few days and uptitration will be attempted again. If again not tolerated, subjects will remain at the last tolerated dose as long as this is at least 1.6 mg QAM. If unable to reach minimum acceptable dose, subjects will be withdrawn from the study.

Visit 3: Pre-MMTT Visit: Subjects will return for provision of Activwatch and review of CGM data from the past 3 weeks. There will be continued data collection regarding glycemic control, variability, frequency of hypoglycemia, physical activity, and sleep duration and quality. Detailed 7-day sleep and insulin diaries will again be provided for the last week. Prior to each post-medication metabolic study day, subjects will also be provided with a 1-day standardized, macronutrient-controlled, weight maintenance diet (45% carbohydrate, 20% protein, 35% fat) with caloric content based on prior DEXA lean body mass and an activity factor as in our previous studies. Depending on scheduling conflicts and the ability to pick up study diet, study staff may provide participants with food recommendations to eat 1 day prior to MMTT with the same macronutrient distribution listed above.

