BCQR intervention: Bromocriptine itself has been available and widely used for Parkinson's Disease and prolactinoma for decades. It was also used for a time for congestive heart failure. The quick release formulation is so far apparently similar in safety and tolerability. Common side effects include mild hypotension, mild fatigue/somnolence, headache, depressed mood, insomnia, nausea, and diarrhea. Less common and more serious side effects have been seen with BCQR including hypersensitivity reactions, hypoglycemia and syncope. There is no increase in CVD. In fact studies so far indicate a protective effect. Bromocriptine is standardly used in young children, adolescents, and adults of all ages with hyperprolactinemia at higher doses than proposed in our study and should be well tolerated. Frequent blood sugar monitoring and contact with study staff will help avoid hypo- or hyperglycemia. Potential benefits include improved glycemic control and decreased insulin requirement, as well as metabolic and vascular benefits related to decreased chronic SNS activity, decreased renin angiotensin system activation, and resetting of the circadian rhythm. Subjects will be withdrawn if they are unable to tolerate the minimum acceptable dose of BCQR (1.6mg QD) or if they experience a predefined serious adverse event (infection related to blood draw or IV placement; severe hypoglycemia during the mixed meal tolerance test (blood glucose < 45 mg/dl), more than one episode of severe hypoglycemia requiring assistance or diabetic ketoacidosis (DKA) while on study drug or other severe reactions possibly or probably related to the study drug). No further data will be collected from withdrawn subjects. All SAEs will be followed until resolution.

Blood Samples: The collection of blood samples may result in temporary discomfort, bruising, bleeding, and on rare occasions, infection. EMLA cream helps to prevent discomfort, and sterile technique helps to minimize these risks.

IV risks: There is temporary discomfort when the needle goes in and 10% of the time there is a small amount of bleeding under the skin that may produce a bruise. Rarely, there is a risk of a blood clot forming or infection. EMLA cream helps to prevent discomfort and sterile technique by experienced CTRC nurses helps to minimize these risks.

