Study stopping and subject discontinuation criteria: The trial will be stopped if >2 subjects meet criteria for individual subject discontinuation [≥ 2 hypoglycemic events requiring assistance or diabetic ketoacidosis (DKA) during a study phase] or if >2 subjects experience a serious adverse event (SAE) possibly or probably related to the study drug. Subjects will be withdrawn if they are unable to tolerate the minimum acceptable dose of BCQR (1.6mg QD) or if they experience a predefined SAE [infection related to blood draw or IV placement; severe hypoglycemia during the MMTT (blood glucose < 45 mg/dl), more than one episode of severe hypoglycemia requiring assistance or DKA while on study drug or other severe reactions possibly or probably related to the study drug]. No further data will be collected from withdrawn subjects. As some withdrawals are accounted for in the recruitment plan, there will be no specific replacement of withdrawn subjects. SAEs will be followed until resolution. Otherwise, withdrawn subjects will follow up with their care providers.

E. Potential Scientific Problems:

Interpretation of results: Based on the basic and clinical literature for BCQR, we expect that BCQR will reduce HGP and lipolysis throughout the day, effectively improving insulin action and reducing glycemic variability, improving glucose tolerance and control as evidenced by lower CGM-glucose and glucose AUC during MMTT, and/or decreasing insulin dose. Any of these results would support the use of BCQR as adjunct therapy in T1D. In addition, the presumed mechanism of BCQR supports an expectation of decreased vascular stiffness and improved endothelial function. These results would further support use of BCQR in T1D, even independent of glycemic benefits, as CVD risk reduction is an important goal in T1D with long term benefits in health outcomes, quality of life, and lifetime medical costs. We further speculate that the effects on sympathetic activation and circadian rhythm may improve sleep quality (thus further improving insulin sensitivity), blood pressure, hypoglycemia awareness, and thus hypoglycemia frequency and/or severity.

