Power and Sample Size: Power analysis and sample size are based on expected changes from the literature and from preliminary data for the primary outcomes for each aim. The sample size for the entire study was based on the power analysis for the subgroup analyses by age, in order to ensure adequate power to detect clinically meaningful treatment effects within each subgroup. In addition, we plan to examine the results by other characteristics (e.g. by obesity level, positive c-peptide status, etc.) in exploratory analyses which are not fully powered, but which may provide insight into heterogeneity in response to the therapy, thus guiding a future clinical trial if results of this study are positive. Desired α is set at 0.05. Since data used for this analysis are from within-subjects comparisons, repeated measures analysis will be used to compare outcome variables after each treatment (placebo, BCQR), adjusting for the randomization assignment of treatment order.

Assessment of Efficacy

The primary efficacy parameters will be change in insulin dose and CGM mean glucose on treatment versus placebo. Secondary efficacy measures will include change in post-MMT glucose and insulin AUC, and change in other CGM parameters (SD, %hyperglycemic, % hypoglycemic). Total daily basal and bolus insulin dose will be obtained at screening, and then at time zero for each medication phase. Insulin diaries will be obtained during the last week of each phase. Change in total, basal, and bolus insulin dose in units per day and total insulin in units per kg per day will be examined between medication phases to determine whether insulin requirements were lower at the end of the BCQR phase than the end of the placebo phase. Similarly, change in mean CGM glucose from the last 2 weeks of each medication phase will be examined to determine if overall mean glucose is decreased while on treatment versus placebo.

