Analysis Plan: All randomized subjects will be included in the analysis using an intention to treat analysis. The change in insulin dose, CGM-glucose and other metabolic parameters will be compared between the placebo and treatment visits in each subject using paired t-tests for univariate comparisons, and using repeated measures linear regression to adjust for covariates including age, diabetes duration, baseline HbA1c, and BMI. An interaction term will be entered into the model to examine whether the effect of treatment on either outcome differs among adults linearly by age, and if there is a significant interaction ($p<0.10$), results will be stratified by age group. We will also use interaction terms to assess whether the effect of treatment differs by BMI. We will also examine whether diabetes duration and initial HbA1c have an effect on outcomes by testing for an interaction between these continuous variables and the change in insulin dose and CGM-glucose. Change in vascular parameters will also be examined using paired t-test and repeated measures regression to determine if the treatment with BCQR affects vascular stiffness or function.

SA1: Effect on metabolic parameters (insulin dose, mean glucose and glycemic variability by CGM, postprandial glucose AUC by MMTT): While there are no published data on the effect of BCQR on insulin dose, prior data on the effect of Metformin⁸⁸ indicate that the change in daily insulin dose is normally distributed with standard error of 2.2 units (SD 7.6) and data from prior studies in adults with T1D performed at our center indicate that the change in total daily insulin dose

over 4 weeks is normally distributed with a standard deviation of 15 – 18.8 units/day. Assuming a SD of 18.8 to be conservative, we will be able to detect a true change in the daily insulin dose of matched pairs of \pm 5.9 units/day with 80% power in the overall group (n=80) and a change of 8.3 units/day within each age group (n=40). In a prior study of the efficacy of BCQR in adult patients with T2D, study participants treated with BCQR experienced a decrease in fasting plasma glucose level of 36.09 mg/dl and a decrease in post-prandial plasma glucose of 14.38 mg/dl after 12 weeks of treatment⁸⁹. In the overall study group, we will be able to detect a change in CGM-glucose of 3.1 mg/dl with 80% power in the entire study group and a change in CGM-glucose of \pm 4.4 mg/dl in each age group, assuming an SD of 10.03 mg/dl.

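### The plan promises an intention-to-treat analysis of all randomised subjects, but its withdrawal and data-collection rules leave some of them with no outcome to analyse

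*Combined protocol and SAP*

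**What the plan says.** Section F, Analysis Plan, sets the analysis population: "All randomized subjects will be included in the analysis using an intention to treat analysis". The analyses it names are paired t-tests for univariate comparisons and repeated measures regression with covariates. Power and Sample Size, also in section F, says the repeated measures analysis is adjusted for treatment order.

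The withdrawal rules stand in three places.

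- Section C, Visit 2, describes uptitration. After a step that is not tolerated, "subjects will be returned to the last tolerated dose for a few days and uptitration will be attempted again". A subject who fails again stays at the last tolerated dose if that is at least the minimum. Otherwise: "If unable to reach minimum acceptable dose, subjects will be withdrawn from the study".
- Section D, BCQR intervention, repeats the dose criterion, adds predefined serious adverse events, and ends: "No further data will be collected from withdrawn subjects".
- Section D, Study stopping and subject discontinuation criteria, repeats both criteria and the same sentence on data. It adds: "As some withdrawals are accounted for in the recruitment plan, there will be no specific replacement of withdrawn subjects".

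On timing, section F, Assessment of Efficacy, says of insulin: "Insulin diaries will be obtained during the last week of each phase". For glucose it uses "change in mean CGM glucose from the last 2 weeks of each medication phase", and gives the purpose as "to determine if overall mean glucose is decreased while on treatment versus placebo". The SA3 primary measures, BrachD and RHI, are taken at the visit that ends each phase (section C, Visit 4).

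The only text on missing data is under Data handling in section D. It describes completing database entries during cleaning. No assumption about unobserved outcomes, no imputation rule and no sensitivity analysis is given.

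**The concern.** An intention-to-treat analysis needs an outcome, or a stated way of handling its absence, for everyone randomised. This plan stops observing withdrawn subjects and gives no such method. Several withdrawal reasons are drug intolerance, severe hypoglycaemia, ketoacidosis or a suspected drug reaction, so missing outcomes may well be related to treatment and response.

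A reader of the final report would take the label to mean that the result covers everyone randomised. It would in fact describe mainly those who stayed on treatment. The two differ if withdrawn subjects respond differently, and without their data nobody can say in which direction.

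**Working it through.** **1. What each kind of withdrawal loses.** Each phase lasts four weeks. The minimum dose is the second-week step, with one re-attempt after a few days. Intolerance withdrawals therefore fall at about weeks 2 to 3, or earlier if the first step is not tolerated.

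| Event | Current phase | Other phase |
|---|---|---|
| Withdrawn in phase 1 uptitration | No insulin diary, BrachD or RHI; at most part of the CGM window | Nothing |
| Withdrawn in phase 2 uptitration | Same | Phase 1 values kept |
| Glucose below 45 mg/dl during the phase 1 meal test | Primary values essentially in hand, since diary and CGM periods are ending and Dynapulse and EndoPAT precede the meal | Nothing |
| Same, during the phase 2 meal test | Essentially in hand | Phase 1 values kept |
| Top step not tolerated, minimum dose tolerated | Complete | Complete; analysed as randomised |

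The first row contradicts the promise outright. Such a subject has no insulin or vascular value for either named method. The second row drops out of the paired t-test. A repeated measures model fitted by likelihood would keep the phase 1 value, but that value gives no within-subject difference, and the fit rests on a missing-at-random assumption that the plan does not state.

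**2. The plan's own figure.** Inputs from section F, SA1: SD 18.8 units/day, n = 80, power 80%, alpha 0.05 (two-sided reproduces the figures).

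Detectable change = SD × (1.960 + 0.842)/√n = 18.8 × 2.802/8.944 = 5.89 units/day (stated 5.9). At n = 40 it is 8.33 (stated 8.3). For CGM glucose with SD 10.03 it is 3.14 and 4.44 mg/dl (stated 3.1 and 4.4). The powered n is the number of completers.

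**3. Documented size of the loss.** Section C, Recruitment, aims for 100 eligible and 80 completing. Section C, Study design, randomises eligible subjects. So 100 − 80 = 20, up to 20% of those randomised, would lack a complete pair from any cause. These targets are for the full study including adolescents.

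**4. Illustration only.** Suppose the effect is 5.9 in subjects who tolerate the drug and k × 5.9 in a fraction p who do not. The all-randomised effect is 5.9 × [(1 − p) + pk], and the completer estimate overstates it by 1/[(1 − p) + pk] − 1. Neither p nor k is in the documents.

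| k | p = 5% | p = 10% | p = 20% |
|---|---|---|---|
| −0.5 | 8.1% | 17.6% | 42.9% |
| 0 | 5.3% | 11.1% | 25.0% |
| 0.5 | 2.6% | 5.3% | 11.1% |
| 1.5 | −2.4% | −4.8% | −9.1% |

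The last row is an understatement.

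**5. Cost of following subjects after they stop drug.** Assume zero effect in intolerant subjects, all intolerance in the BCQR phase, SD 18.8 unchanged, and half of the intolerant subjects placebo-first. That half gains a pair; the BCQR-first half still has no placebo value. Paired-t power:

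- 10 intolerant, no other losses: 90 completer pairs at 5.9 give 83.8%. With 95 pairs the mean is 5.9 × 90/95 = 5.59 and power is 81.8%.
- 10 intolerant, 10 other losses: 80 pairs at 5.9 give 79.2%. With 85 pairs the mean is 5.9 × 80/85 = 5.55 and power is 76.8%.
- 20 intolerant: 79.2% becomes 74.5%, with 90 pairs and mean 5.9 × 80/90 = 5.24.

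The loss is about 2 to 5 points. The paired estimate would still overstate the all-randomised effect: 5.59/5.31 is 5% in the first case and 5.24/4.72 is 11% in the third.

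**The case against.** This is a pilot meant to give preliminary data, and the efficacy text asks an on-treatment question for glucose. The recruitment plan openly allows for losses, and power is computed on completers. Order-adjusted repeated measures analysis is already planned, and nothing makes the paired t-test primary. Subjects who tolerate the minimum dose but not the top step stay in and are analysed as randomised, which is real intention-to-treat content. A withdrawal during the meal test costs little or nothing for that phase. The rule is applied blind, so some withdrawals will fall in the placebo phase.

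All of this stands, and it narrows the point. It does not remove the conflict. Allowing for losses in recruitment protects power, not the claim that everyone is analysed. If the on-treatment question is the intended one, the intention-to-treat sentence is the part that is wrong.

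A reader might infer from the illustration that the result will be inflated by 25% or more. The documents do not support that. It would need all 20 planned losses, whatever their cause, to be BCQR intolerance with zero or reversed effect. With a larger effect in withdrawn subjects the estimate would be too small. Nor do the documents support reading every withdrawal as a total loss of data.

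**Conclusion.** The plan claims a property that its design cannot deliver. Subjects withdrawn during phase 1 uptitration have no insulin or vascular outcome in either phase and at most part of one CGM window. Those withdrawn during phase 2 uptitration keep phase 1 values only. The one documented size is up to 20 of 100 randomised without a complete pair, assuming that all eligible subjects are randomised and the recruitment targets are met. The share due to intolerance, and the size and direction of any bias, cannot be known from the documents. The percentages above follow from assumed values and are not evidence.

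The point should be fixed because the wording would mislead about whom the result describes and the repair is cheap. It is not a finding that the trial's estimate is biased, and it gives no view on the withdrawal rule itself.

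**What to change.** Reconcile Visit 2, the two section D passages and the Analysis Plan by choosing one target.

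**Option 1: on-treatment target.** Drop the intention-to-treat label. Describe the analysis set as randomised subjects with end-of-phase data, and say that the result describes those who stayed on treatment. Label the paired t-test a completer analysis. Report withdrawals by treatment and phase. The cost is wording only; the downside is a narrower claim.

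**Option 2: all-randomised target.**

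- Leave the drug-stopping criteria unchanged. Amend the no-further-data sentence so that consenting subjects who stop drug still give that phase's insulin diary and CGM.
- Make the already planned order-adjusted repeated measures model the main analysis, fitted by likelihood to all subjects with any end-of-phase value. State its missing-at-random assumption.
- Add a not-at-random sensitivity analysis. Set the BCQR-placebo difference in withdrawn subjects to zero, then vary it over a stated range that includes negative values, for example −0.5 to 1.5 times the estimate.
- Label SA3 (BrachD, RHI) completer-based.

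Option 2 costs a short amendment and one diary and one CGM download for each subject who stops drug, at most about 20. Its downsides are the dilution shown above and data still missing for those withdrawn in phase 1.

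Under either option, say how a partial CGM window is used.

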Research Design and Methods: We propose to address the study hypotheses and aims with a double-blinded, random-order, placebo-controlled cross-over design study in T1D. The intervention will consist of 4 weeks of treatment with BCQR (Cycloset™) and 4 weeks of placebo separated by a ≥ 4 week washout. Interventions of this duration have been found to be adequate for detecting changes in vascular function, cardiac autonomic function, and glucose control for other anti-diabetic and fatty acid lowering agents (eg⁶⁸⁻⁷²). Most studies with BCQR in T2D have longer in duration. However, two studies demonstrated improved glucose and/or insulin levels after administration of a single dose⁷³ or 4-8 weeks of daily dosing⁷⁴. In addition, the mechanism predicts acute changes in glucose control and vascular parameters. The shorter duration is proposed here to minimize the cost and subject burden in this pilot study.

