Recruitment: Ultimately 133 T1D subjects (50% male, 50% adolescent) will be enrolled with the goal of having 100 eligible and completing 80 (see power analysis). Recruitment will begin year 1 for the adult cohort and an adolescent cohort will be added in year 2. We will begin with a mass mailing to the established CACTI cohort of >600 adults with T1D mailing list established through [name] clinical relationship. In addition, a co-investigator from the Barbara Davis Center adult T1D clinic ([name]) is included specifically for recruitment purposes. Through these approaches we hope to have the full adult cohort recruited, but not completed, by the end of year 1. Late in year 1, any adverse events will be thoroughly reviewed by the safety officer to assess for any safety concerns (in particular hypoglycemia) prior to submitting an amendment to broaden the age range to add the adolescent cohort. However, we do not expect to encounter significant safety issues since higher doses and much longer durations of standard release bromocriptine are widely used in adults and children for other medical conditions. Beginning year 2, adolescent recruitment will consist of patients from the Barbara Davis Center for Childhood Diabetes (BDC) where co-investigator [name] is a medical provider and has a weekly clinic. [name] has excelled when recruiting adolescent T1D patients as she currently recruits for multiple protocols researching the abnormalities associated with T1D. Furthermore, [name] holds a weekly Endocrine Clinic and is a provider in the Lifestyle Medicine Clinic at the Children's Hospital of Colorado where she has a clinical relationship with many patients with T1D and other endocrine disorders. Co-investigator [name] is also a physician at the BDC and holds multiple weekly clinics with T1D patients. IRB approved flyers will be placed in private Endocrine clinics in the Denver Metro area. Through these approaches we hope to have the full adolescent cohort recruited. We include both lean and obese participants as BMI and age-based differences in IR, glycemic control, hormone levels, sleep patterns and diabetes duration may impact response to BCQR. This recruitment strategy has been used successfully for our similarly powered individual ongoing studies.

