Investigational product: Bromocriptine Quick Release (Cycloset™): Bromocriptine itself has been available and widely used for Parkinson's disease and prolactinoma for decades. It was also used for a time for congestive heart failure. BCQR is FDA approved for adult and T2D is currently undergoing safety and efficacy trials in T2D adolescents. BCQR has a similar side effect profile to standard formulations of bromocriptine. Common side effects include mild hypotension, mild fatigue/somnolence, headache, depressed mood, insomnia, nausea, and diarrhea. Less common and more serious side effects have been seen with BCQR including hypersensitivity reactions, hypoglycemia and syncope. Bromocriptine is

standardly used in young children, adolescents, and adults of all ages with hyperprolactinemia at higher doses than proposed in our study and should be well tolerated. To assess the hypotensive side effect of Bromocriptine, blood pressure measurements, as outlined by the CDC to access orthostatic hypotension, will be collected at every study visit for the adolescent cohort only. Continuous glucose monitoring and contact with study staff will help avoid hypo- or hyperglycemia. Potential benefits include improved glycemic control and decreased insulin requirement, as well as metabolic and vascular benefits related to decreased chronic SNS activity, decreased renin angiotensin system activation, and resetting of the circadian rhythm.

Study design: Eligible subjects will be randomized to order of treatment (placebo followed by BCQR vs. BCQR followed by placebo). Belmar Pharmacy will be supplying the study drug (BCQR 0.8 mg and identical placebo tablets). The study timeline for Phase 1 is illustrated in **Fig 6**. Phase 2 consists of visits identical to Phase 1 numbered 5-7.

Visit 1: Screening visit:

Prescreening will be done by phone or in conjunction with a clinical diabetes visit. The full screening visit will include the consent process, history, physical exam, and screening labs (HbA1c, comprehensive

Figure 6: Study timeline (for each medication phase)

[figure not shown]
Stage day: 0

14

~21

~26

~28

metabolic panel, TSH (adult participants only), urine microalbumin, lipids). All females will also have a pregnancy test and detailed menstrual history. Adult females will have FSH and estradiol to determine pre- or postmenopausal status.

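### The crossover's order adjustment has no stated form, and the tests and covariates named in the Analysis Plan do not take out a period effect

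*Combined protocol and SAP*

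**What the plan says.** Section C describes a "random-order, placebo-controlled cross-over design study in T1D" with two 4-week phases and a washout of at least 4 weeks, and its Study design paragraph adds: "Eligible subjects will be randomized to order of treatment". The allocation ratio and method are not stated. The Recruitment paragraph expects 133 to be "enrolled with the goal of having 100 eligible and completing 80".

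Treatment order appears in the analysis text once, in Section F under Power and Sample Size: a repeated measures analysis of the outcomes after each treatment, "adjusting for the randomization assignment of treatment order". Nothing says how order enters the model.

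The Analysis Plan paragraph does not repeat this. It compares placebo and treatment visits "using paired t-tests for univariate comparisons, and using repeated measures linear regression to adjust for covariates including age, diabetes duration, baseline HbA1c, and BMI". For the vascular measures: "Change in vascular parameters will also be examined using paired t-test and repeated measures regression". It also says: "All randomized subjects will be included in the analysis using an intention to treat analysis". Under the stopping criteria in Section D, however: "No further data will be collected from withdrawn subjects". No section names a period term.

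**The concern.** Every subject gives one value after BCQR and one after placebo, at different times. If outcomes drift between phase 1 and phase 2 for any reason other than treatment, the BCQR-minus-placebo difference carries that drift with opposite signs in the two orders. The paired t-test treats this as noise. Age, diabetes duration and baseline HbA1c take one value per subject, so with complete pairs their main effects cancel from the within-subject contrast. BMI is not labelled as baseline, but even if re-measured it would not stand in for period.

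The promised order adjustment could solve the problem or do nothing, depending on its form. At stake are power for the primary outcomes and, if the two orders finish with unequal numbers, the treatment estimate itself.

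**Working it through.** **The plan's own figures (Section F, SA1).** With two-sided α of 0.05 (sidedness is assumed) and 80% power, the detectable change is (1.960 + 0.842) × SD/√n.

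- Insulin dose, SD 18.8: 5.89 units/day at n = 80 and 8.33 at n = 40. The plan states 5.9 and 8.3.
- CGM glucose, SD 10.03: 3.14 mg/dl at n = 80 and 4.44 at n = 40. The plan states 3.1 and 4.4.

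These reproduce. None has a period component.

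**Model.** Let τ be the treatment effect and π the phase 2 minus phase 1 shift. The difference BCQR minus placebo has mean τ + π for placebo-first subjects (n2 of them) and τ − π for BCQR-first subjects (n1), with N = n1 + n2. Therefore:

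- mean of the paired differences = τ + π(n2 − n1)/N;
- SD seen by the paired test = √(SD² + 4f(1 − f)π²), with f = n1/N, which is √(SD² + π²) when n1 = n2.

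**What an order main effect does.** It moves both phases of a subject by the same amount and so cancels from the difference. Fitted mixed models on simulated data (SD 10.03, π = 5, no treatment effect) confirm this:

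| Model | 40/40 estimate (SE) | 48/32 estimate (SE) |
|---|---|---|
| Treatment only (same as paired t-test) | −3.059 (1.223) | −0.576 (1.058) |
| + age + BMI | −3.059 (1.223) | −0.576 (1.058) |
| + order main effect + age + BMI | −3.059 (1.223) | −0.576 (1.058) |
| Treatment + period | −3.059 (1.137) | 0.108 (1.015) |

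Each column is one simulated data set. What matters is which rows agree. Regressing the paired difference on order coded symmetrically reproduces the last row, so that form of order adjustment would work.

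**Power with equal completers, by hand.** Take CGM glucose at 40/40, τ = 3.1 and π = 5. The SD seen is √(10.03² + 5²) = 11.21, and the reported SE is 11.21/√80 = 1.253. The rejection threshold is 1.990 × 1.253 = 2.494. The mean itself still varies with SE 10.03/√80 = 1.121, because π is a fixed shift. Power is about Φ((3.1 − 2.494)/1.121) = Φ(0.54) = 0.71. Simulation (200,000 trials per cell) gives:

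| Assumed shift | 1 | 2 | 3 | 5 | 8 |
|---|---|---|---|---|---|
| CGM, 40/40, effect 3.1: paired power | 0.777 | 0.767 | 0.752 | 0.704 | 0.586 |
| Same, with period term | 0.78 | 0.78 | 0.78 | 0.78 | 0.78 |
| Paired type I error | 0.048 | 0.046 | 0.040 | 0.029 | 0.013 |
| CGM, 20/20, effect 4.4: paired power | – | 0.760 | 0.743 | 0.693 | 0.572 |
| Same, with period term | – | 0.77 | 0.77 | 0.77 | 0.77 |

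Insulin dose, effect 5.9 and shift 5.9 units/day, 40/40: 0.762 paired against 0.791 with period (SD 18.8), and 0.914 against 0.935 (SD 15).

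**Bias with unequal completers.** At 45/35 with a 5 mg/dl shift, the bias in size is 5 × 10/80 = 0.625 mg/dl, and 0.625/3.1 = 20% of the effect the study is sized for. Paired type I error there is 0.054, against 0.049 with period modelled.

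**How likely is such a split?** Suppose 80 of 100 randomized subjects complete, unrelated to order. A split of 45/35 or worse then has probability 0.023 if exactly 50 were randomized to each order, and 0.314 under simple randomization. Within one age group (40 of 50), 23/17 or worse has 0.074 and 0.430; the bias at a 5 mg/dl shift is 5 × 6/40 = 0.75 mg/dl.

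**The case against.** The strongest reply is that order adjustment is already promised. The regression in the Analysis Plan can be read as that repeated measures analysis, and its covariate list is open-ended, so a period term is not ruled out. That is fair: a reader who infers that the plan ignores order would be wrong. The promise is still incomplete, because its most literal form, an order main effect, changes nothing.

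A reader might also infer that the primary estimates are biased. The documents do not support that. They report no period shift and no imbalance, and with equal completers the shift cancels from the estimate. Phase 2 visits repeat those of phase 1, CGM support recurs in each phase, and a washout separates them. The larger power losses need shifts of 5 or 8 mg/dl, which are 1.6 and 2.6 times the 3.1 mg/dl effect.

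Nor do the documents support a claim of inflated false-positive rates. With equal completers the paired test is conservative, and at 45/35 with a 5 mg/dl shift it is close to nominal. Clear inflation needs something more extreme: 48/32 with a 5 mg/dl shift gives about 0.095. An order adjustment coded so as to keep the bias could also inflate the rate, but nothing in the text points to such coding.

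**Conclusion.** The point holds as an improvement that costs almost nothing, not as a flaw that undermines the trial. The paired t-tests ignore period, the listed covariates do not remove it, and the order adjustment is effective only in a form that the plan does not state.

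The main consequence is lost power for CGM glucose: 1 to 3 points at shifts of 2 to 3 mg/dl, about 8 at 5 mg/dl and about 19 at 8 mg/dl. For insulin dose the loss is about 3 points at a 5.9 units/day shift (2 if the SD is 15). Bias arises only if completers per order are unequal, in proportion to the shift and the imbalance. All shifts and splits here are assumptions; the SDs, effects and numbers of completers are the plan's.

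**What to change.** In the Analysis Plan, for both the metabolic and the vascular outcomes, name as primary a mixed model with fixed effects for treatment, period and sequence and a random subject effect. State that this is what the order adjustment under Power and Sample Size means. Keep the paired t-test as descriptive.

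The model can also use subjects who have only one phase, which a paired test drops, so it fits the commitment to analyse all randomized subjects. The gain in precision is small. Adding 20 phase-1-only subjects (10 per order) to 80 pairs takes the CGM standard error from 1.121 to between 1.116 and 1.093, for assumed intraclass correlations of 0.9 to 0.5.

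The cost is a change of wording and one degree of freedom. Period and order are known for every subject, so no new data are needed, and the sample size stands.
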